16.4.2 Guidance on monitoring participants with infections

All infections that develop during the study will be reported as adverse events on the respective eCRF pages. Treatment and additional evaluations will be performed at Investigator discretion. The Investigator should remind the participant of the risk of infections and instruct them to report any symptoms of infections promptly. In the case of suspected or confirmed serious (CTCAE, Grade 3-4) or atypical infection, study drug interruption should be considered. The Investigator should inform the Novartis Medical Advisor and/or a Study Team member of any such cases. When evaluating a participant with a suspected infection, the most sensitive tests available should be used (i.e. that directly detect the pathogen, as with PCR). The Investigator should consider early treatment with specific antimicrobial therapy based on clinical diagnosis or suspicion thereof in consultation with infectious disease experts, as appropriate. The Investigator should inform the Novartis Medical Advisor and Global Study Team of any such cases. Investigators should consider the added immunosuppressive effects of corticosteroid therapy for treatment of clinical relapses/attack and increase vigilance regarding infections during such therapy and in the weeks following administration.

Hepatitis B Virus (HBV)

There were no reports of HBV reactivation in patients with MS treated with ofatumumab. However, HBV reactivation, in some cases resulting in fulminant hepatitis, hepatic failure, and death, has occurred in patients being treated with ofatumumab for chronic lymphocytic leukemia (CLL) (at significantly higher intravenous doses than the 20 mg dose in this study) and in patients treated with other anti-CD20 antibodies. HBV screening is required in all study participants, including hepatitis B surface antigen (HBsAg) and hepatitis B core antibody (HBcAb) testing. These can be complemented with other appropriate markers as per local guidelines. Participants with positive hepatitis B serology (either HBsAg or HBcAb) should consult a liver disease expert before the start of treatment and should be monitored and managed following local medical standards to prevent HBV infection or reactivation. In participants with suspicion of HBV infection (active/reactivation) during the study, laboratory testing for HBV should be done. For participants with positive hepatitis B serology (either HBsAg or HBcAb), the Investigator should consult a liver disease expert and participants should be monitored and managed following local medical standards to prevent HBV infection or reactivation. In participants who develop infection or reactivation of HBV while receiving study drug, immediately discontinue study drug and institute appropriate treatment and follow-up.

16.4.3 Guidance on monitoring of participants with low immunoglobulin levels

During the study, immunoglobulin levels (IgG and IgM) will be measured according to the schedule in Table 8-1. If IgG levels drop below 300mg/dL (Agarwal and Cunningham-Rundles 2007), the Investigator should evaluate participant for any potential infections and monitor on a regular basis (refer to [Section 16.4.2](#)). Consider interrupting or discontinuing study treatment if a participant with low IgG as defined above develops a serious opportunistic

infection or recurrent infections, or if prolonged hypogammaglobinemia requires treatment with intravenous immunoglobulins. Immunoglobulin substitution therapy as per local medical practice is allowed and all relevant data must be recorded on the appropriated eCRFs. In case of treatment interruption, re-initiation of the study drug is subject to Investigator's discretion. Care should be taken to re-initiate study treatment according to planned dosing schedule in relation to the participant's W0 injection to ensure continuity and regularity of study visits and assessments. Participants that are prematurely discontinued should have the EOS visit as early as possible and continue into the Post-treatment Follow-up, please refer to assessment schedule [Table 8-2](#).

16.4.4 Guidance on immunization

The safety of and ability to generate a primary or anamnestic response to immunization with live, live-attenuated or inactivated vaccines during ofatumumab treatment has not been investigated. The response to vaccination could be impaired when B-cells are depleted. It is recommended that the Investigator reviews the participant's immunization history as part of the initial Screening procedure for a participant being considered for treatment with ofatumumab. Because vaccination with live-attenuated or live vaccines is not recommended during treatment with ofatumumab and after treatment discontinuation until B-cell repletion, all immunizations must be administered according to immunization guidelines at least 4 weeks prior to initiation of ofatumumab for live or live-attenuated vaccines, and whenever possible, at least 2 weeks prior to initiation of ofatumumab for inactivated vaccines (including Sars-CoV-2 vaccines) . Hepatitis B vaccination should be considered prior to administration of ofatumumab in participants with risk factors for hepatitis B infection or in areas with a high prevalence of hepatitis B, as per local area treatment guidelines. Immune suppression of B cells is expected to affect the response to vaccination, and thus during treatment with ofatumumab, vaccination (non-live vaccines) may be less effective.

Sars-CoV-2 Vaccinations

SARS-CoV-2 vaccinations (e.g. inactivated, viral-vector-, or mRNA) that have been permitted for use by a local Health Authority are allowed. Permitted use includes full approval, conditional approval, emergency use authorization, provisional/temporary/interim authorization by Health Authority that are administered outside of a SARS-CoV-2 clinical trial to evaluate the effectiveness or safety of a SARS-CoV-2 vaccine.

Additional guidance on permitted use of SARS-CoV-2 vaccinations may be made available separately taking into consideration the SARS-CoV-2 vaccine prescribing information, ofatumumab/SARS-CoV-2 vaccination recommendations and health authority guidance. Risk/benefit ratio for SARS-CoV-2 vaccination must be evaluated on a case-by-case basis by the Investigator.

SARS-CoV-2 vaccination status is to be recorded on appropriate eCRF.

## Document History – Changes compared to previous final version of SAP

Date	Time point	Reason for update	Outcome for update	Section and title impacted (Current)
12-Jun-2024	Prior to DB lock	Creation of final version	N/A - First version	NA
26-Feb-2025	Prior to DB lock	Creation of Amendment 1	

Remove analyses on new or enlarged T2 lesions during onset period;

Remove exposure adjusted incidence rates for TEAEs and serious TEAEs;

[REDACTED]

Revise lab parameters in Table 5-3 that are not applicable in this study

	

Section 2.6.2 Statistical hypothesis, model, and method of analysis

Section 2.7.1 Adverse events (AEs),

Section 5.4.3 Exposure adjusted incidence rate for TEAEs removed

Section 5.3.3 CTCAE grades for laboratory parameters

....				

## List of abbreviations

AE	Adverse Event
ALP	Alkaline phosphatase
ALT	Alanine aminotransferase
ARR	Annualized relapse rate
AST	Aspartate aminotransferase
ATC	Anatomical Therapeutic Chemical
CI	Confidence Interval
CRF	Case Report Form
CSR	Clinical Study Report
CTCAE	Common Terminology Criteria for Adverse Events
DMT	Disease modifying therapy
eCRS	Electronic Case Retrieval Sheet
EDSS	Expanded Disability Status Scale
EOS	End of Study
FAS	Full Analysis Set
FS	Functional System
Gd	Gadolinium
IA	Interim Analyses
IgG	Immunoglobulin G
IgM	Immunoglobulin M
KM	Kaplan-Meier
LDD	Last dose date
LLN	Lower limit of normal
MedDRA	Medical Dictionary for Drug Regulatory Affairs
MRI	Magnetic Resonance Imaging
MS	Multiple sclerosis
NB	Negative binomial
NMPA	National Medical Products Administration
PD	Pharmacodynamic(s)
PDS	Programming datasets specifications
PK	Pharmacokinetics
PT	Preferred term
RAP	Reporting & Analysis Process
RMS	Relapsing MS
SAE	Serious AE
SAF	Safety Set
SAP	Statistical Analysis Plan
SAS	Statistical Analysis System
SCR	Screened subjects set
SOC	System Organ Class
TBL	Total Bilirubin
TEAE	Treatment emergent AE
TFLs	Tables, Figures, Listings

ULN	Upper Limit of Normal
WHO	World Health Organization

## 1 Introduction

The purpose of this Statistical Analysis Plan (SAP) is to describe the implementation of the statistical analysis planned in the protocol for study COMB157G2402.

There will be one report resulting from this SAP: the clinical study report (CSR) of the G2402 study. This report will be generated once and referred to as final CSR. The final CSR will be completed after the final database lock.

This document is consistent with the current study protocols (version 00 original protocol).

### 1.1 Study design

This is a 12-month, open-label, prospective, multi-center, single-arm, interventional study to evaluate the efficacy and safety of ofatumumab (OMB157) in approximately 100 adult participants with RMS in China.

The study consists of three periods (see [Figure 1-1](#)): Screening, Treatment, and Post-treatment Follow-up.

#### Screening (up to 30 days):

After signing the informed consent, participants will enter the Screening period to determine eligibility according to the inclusion and exclusion criteria. The Investigator must ensure that participants meet all the inclusion and none of the exclusion criteria to be eligible for the study. If a participant is declared a screen failure, he/she may be re-screened and all assessments must be repeated, with the possible exception of the MRI (if the initial screening MRI was completed within the last 3 months). For details, refer to [\[Protocol Section 8.1\]](#).

#### Treatment (12 months):

During the Treatment period, all eligible participants will receive initial dosing with ofatumumab 20 mg s.c. injection at Baseline/Week 0 (BL/W0), W1 and W2, followed by subsequent monthly dosing starting at W4 (Month 1/M1; a study month is defined as 28 days). The first s.c. injection at W0 will be administered

All participants will have an End of Study (EOS) visit at the end of the Treatment period, when a participant has reached the maximum of 12-month treatment, or at the time a participant prematurely discontinues study treatment. After study treatment discontinuation, participants may initiate alternative MS therapy according to local standard of care if clinically indicated (refer to [\[Protocol Section 9.3\]](#)).

#### Post-treatment Follow-up (6 months):

All participants, except for completers who decide to continue with commercially available ofatumumab treatment, will be followed up in the Post-treatment Follow-up period for 6 months

after last study drug dose ([Protocol Table 8-2]). The Post-treatment Follow-up visits should be scheduled relative to the EOS visit and will occur at EOS+3 months and EOS+6 months (End of Post-treatment Follow-up). If a participant prematurely discontinues from Post-treatment Follow-up, the End of Post-treatment Follow-up visit should be arranged as soon as possible. Investigators may continue to follow participants outside of this study at his/her discretion (for example, if participants have not repleted their B-cells at the end of Post-treatment Follow-up).

Throughout the study periods, participants may have unscheduled visits due to a suspected MS relapse, an acute illness of undetermined cause, for other reasons, or at the discretion of the Investigator (refer to [Protocol Section 8.3.1]).

**Figure 1-1 Study Design**

## 1.2 Study objectives, endpoints and estimands

**Table 2-1 Objectives and related endpoints**

Objective(s)	Endpoint(s)
Primary objective(s) 

To evaluate the effect of ofatumumab 20 mg monthly s.c. on annualized relapse rate (ARR) in participants with RMS

	Endpoint(s) for primary objective(s) 

Annualized relapse rate (ARR, based on frequencies of confirmed relapses)

Secondary objective(s) 

To evaluate the safety and tolerability of ofatumumab 20 mg monthly s.c. in participants with RMS

To evaluate the effect of ofatumumab 20 mg monthly s.c. on MRI lesions in participants with RMS

	Endpoint(s) for secondary objective(s) 

Adverse events, including injection-related reactions;

Laboratory data and vital signs.

Number of Gd-enhancing T1 lesions per MRI scan ;

Number of new/enlarging T2 lesion per year (annualized T2 lesion rate);

Change in T2 lesion volume compared to baseline.

### **1.2.1 Primary estimand(s)**

Not applicable.

## **2 Statistical methods**

### **2.1 Data analysis general information**

The Novartis statistical and programming teams will conduct the CSR analysis as planned in this SAP, unless otherwise specified.

The Statistical Analysis System (SAS) 9.4 and/or R 3.6.1 or higher versions will be used.

Unless otherwise stated, summary tables/figures/listings will be on all subjects in the respective analysis sets. Categorical data will be presented as frequencies and percentages. For continuous data, mean, standard deviations, median, 25th and 75th percentiles (optional), minimum and maximum will be presented.

For efficacy analyses other than MRI related analysis, all available data until the end of the Treatment Period, i.e. excluding the data collected during the Post-treatment Follow-up period, will be considered and no other cut-offs will be applied. For MRI related analysis, all available data from scheduled scans will be included, i.e. also including the ones taken in Post-treatment Follow-up period for the prematurely discontinued participants.

For safety analyses, unless otherwise specified, only data up to and including the safety cut-off of 100 days after the last administration of study treatment will be considered. Therefore, observations obtained beyond safety cut-off will be excluded from such analyses. Nevertheless, all serious adverse events (SAE) and all deaths, regardless of the safety cut-off will be summarized.

### **2.1.1 General definitions**

Below summarize some general definitions to be used in the rest of the document.

**Table 2-1 General definitions**

Study treatment/Study drug	The investigational drug (ofatumumab) will be referred as study treatment or study drug.
Date of first administration of study drug/first dose date	The first dose date of active study drug (ofatumumab) administration.
Date of last administration of study drug/last dose date	The last dose date of active study drug (ofatumumab) administration.

Study Day 1 or Day 1	The date of first administration of study drug/first dose date.
Study Day	All other study days will be labeled relative to Day 1. For events with dates on or after Day 1, study day for the event is calculated as (event start date – first dose date + 1). For events with dates before Day 1, study day for the event is calculated as (event start date – first dose date).  Day 0 will not be used.
Duration of an event	Duration of an event is calculated as (event end date – event start date +1).
1 month	30 days; to be used in defining 3-month confirmed disability progression.
4 weeks	28 days; to be used in determining target days of scheduled visits. It is based on the scheduled injection frequency for ofatumumab (during the maintenance phase).
Day post-study drug discontinuation	Day post-study drug discontinuation for a particular event is calculated as (event start date – study drug discontinuation date).
Baseline	Baseline is the last assessment with non-missing value obtained prior to the first administration of study drug. No visit windows will be needed for the identification of baseline assessment.  For pulse and blood pressure vital sign values, if 3 measurements were taken on the last visit prior to the first administration of study drug, then the baseline is the average of the non-missing values of them.
On-treatment period	For participants received ofatumumab, on-treatment period includes days from the first injection date until 30 days after the last injection date. The on-treatment definition applies to efficacy analyses and B-cell summaries only.  For calculation of compliance to study drug administration, similar definition of on-treatment period will be used.
Safety cutoff (off-treatment)	The safety cutoff is defined as 100 days after the last dose administration of study drug (or EOS for participants continue with commercial ofatumumab immediately after EOS, or min (last dose of study medication + 100 days, date of switching to another DMT - 1) for participants who have such switch in the Post-treatment Follow-up period). Unless

	explicitly otherwise stated, only data up to and including the safety cut-off will be included in the analysis and data beyond this time point for a given subject will be excluded. The safety cutoff applies to safety analyses only.
Nominal visits	Nominal visits are defined as all scheduled visits as per the clinical study protocol including the EOS visits. The definition of nominal visit excludes unscheduled visits.
End of Study (EOS)	EOS, used in the context of individual participants, refers to EOS visit.
End of treatment period date	This date is the date of discontinuation/study phase completion as recorded in the Study disposition eCRF page.
Last assessment on drug	It is the last assessment with non-missing value taken before or on the date of last administration of study drug. No visit windows will be needed for the identification of the last assessment on drug evaluation.

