Participants, except for those who will continue with commercially available ofatumumab treatment, will enter the 6-month Post-treatment Follow-up period after EOS as described in [Table 8-2](#).

As per [Section 4.6](#), during a Public Health Emergency as declared by local or regional authorities i.e. pandemic, epidemic or natural disaster that limits or prevents on-site study visits, alternative methods of providing continuing care may be implemented by the investigator as the situation dictates. If allowable by a local health authority and depending on operational capabilities, phone calls, virtual contacts (e.g. tele consult) or visits by site staff/home nursing staff to the participant's home, can replace on-site study visits, for the duration of the disruption until it is safe for the participant to visit the site again.

Table 8-1 Assessment Schedule, Screening and treatment

Period	Screening	Treatment							Treatment	
Visit Name	Screening	BL/W0	W1 (Phone Interview)	W2 (Phone Interview)	W4	M3	M6	M9	M12/EOS	Unscheduled Visit ¹
Days	-30 to -1	-	7	14	28	84	168	252	336	-
Informed consent	X									
Demography, Height	X									
Inclusion / Exclusion criteria	X	X ²								
Medical history/current medical conditions	X									
MS History/Treatments	X									
COVID-19 vaccination status	X	X ³	X	X	X	X	X	X		
Physical Examination	S	S ³			S		S		S	S
Weight, Vital Signs	X	X ⁴			X	X	X	X	X	X
Electrocardiogram (ECG)	X									
Hematology	X ⁵				X	X	X	X	X	
Clinical Chemistry	X ⁵				X	X	X	X	X	
Urinalysis	X ⁵				X		X		X	
Serological markers for hepatitis B ⁶	X ⁵									
HIV antibody screen ⁷	X ⁵									
Syphilis screen ⁷	X ⁵									
Tuberculosis screen ⁷	X ⁵									
Pregnancy and assessments of fertility ⁸	X ⁵	X ³			X	X	X	X	X	
Contraception Status ⁹	X	X ³	X	X	X	X	X	X	X	
MS relapse	X	X ³	X	X	X	X	X	X	X	X
MRI	X					X			X ¹⁰	

Period	Treatment										Treatment
	Screening	BL/W0	W1 (Phone Interview)	W2 (Phone Interview)	W4	M3	M6	M9	M12/EOS	Unscheduled Visit ¹	
Visit Name	Screening										
Days	-30 to -1	-	7	14	28	84	168	252	336	-	
Adverse Events	X	X ³	X	X	X	X	X	X	X	X	
Prior/Concomitant Medications ¹¹	X	X ³	X	X	X	X	X	X	X	X	
Surgical/medical procedures	X	X ³	X	X	X	X	X	X	X	X	
Sample for B-cells ¹²	X	X ³			X	X	X		X		
Sample for IgG and IgM ¹²	X						X		X		
Drug dispensation		S			S	S	S	S			
Drug administration ¹³		X	X	X	Monthly, except for M12/EOS						
Participant diaries ¹⁴					X						
Participant Diary Review					X	X	X	X	X		

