¹⁰ MRI scan at the End of Study (EOS) is needed if there was no MRI scan in the last 3 months.

¹¹ Including corticosteroids used to treat MS relapse; any newly started MS treatment as applicable (for participants who have discontinued study medication).

¹² The assessments (samples taken for IgG and IgM, B-cells) should be completed prior to study drug administration.

¹³ The first s.c. injection at W0 will be administered [REDACTED]

¹⁴ Study treatment administration (including date and time of s.c. injections) and home pregnancy testing (date and results) for women of childbearing potential will be recorded for each home injection. Other information (e.g. AEs) will be recorded continuously.

¹⁵ Phone interview will be performed by site staff for W1 and W2, and then every month starting from W4 between scheduled visits. The interview should take place around time of the monthly s.c. self/home injection to query about any new or worsening symptoms warranting an unscheduled visit, injection reactions, results of home pregnancy testing and compliance with contraception requirements.

¹⁶ Phone interview/virtual visits are also applicable to the scheduled visits for participants who exceptionally cannot come to the study site for a face-to-face examination due to a Public Health Emergency (e.g. restricting the subject's general access to sites).

Table 8-2 Assessment Schedule, Post-Treatment Follow-up

Period	Post-Treatment Follow-Up		
Visit Name	V1 ¹	End of FU ^{1,2}	Unscheduled Visit ³
Days	EOS+3 months	EOS+6 months	NA
Weight, Vital Signs	X	X	X
COVID-19 vaccination status	X	X	
Physical Examination	S	S	S
Clinical Chemistry	X	X	
Hematology	X	X	
Urinalysis	X	X	
Pregnancy Test (serum) ⁴	X	X	
Contraception Status ⁵	X	X	
Sample for B-cells	X	X	
Sample for IgG and IgM	X	X	
MS relapse	X	X	X
MRI		X ⁶	
Concomitant medications ⁷	X	X	X
Surgical/medical procedures	X	X	X
Adverse Events	X	X	X
Phone interview/virtual visit ^{8,9}	Monthly between scheduled visits		
Post Treatment Part Completion		X	

^X Assessment to be recorded in the clinical database or received electronically from a vendor

^S Assessment to be recorded in the source documentation only

¹ Visits 1 and end of FU are applicable to all participants, except for completers of the Treatment period who decide to continue with commercially available ofatumumab treatment.

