12.5.2 Safety endpoints

For all safety analyses, the safety set will be used. Unless explicitly stated otherwise, only data up to and including the safety cut-off of 100 days after permanent study treatment discontinuation or treatment completion (or EOS for participants continue with commercial ofatumumab immediately after EOS, or min(last dose of study medication + 100 days, date of switching to another DMT - 1) for participants who have such switch in the PT FU) will be

included in the analysis and data beyond this time point for a participant will be excluded from safety analysis.

The assessment of safety data will be primarily based on the frequency and percentage of adverse events (including death and non-fatal serious adverse events). Additional safety assessments such as laboratory tests, physical examination (including examination of skin), and vital signs will be analyzed. Clinically significant findings in these additional safety assessments will be reported as adverse events and analyzed as such. The detailed analyses of additional safety assessments will be defined in the SAP.

Adverse events

Treatment-emergent adverse events including serious adverse events and deaths will be summarized up to and including the safety cut-off.

The number (and percentage) of participants with treatment emergent adverse events (events started after the first dose of study medication or events present prior to start of treatment but increased in severity based on preferred term) will be summarized in the following ways:

- by primary system organ class and preferred term.
- by primary system organ class, preferred term and maximum severity.

Separate summaries will be provided for adverse events related to study treatment, death, serious adverse events, and other significant adverse events leading to interruption or discontinuation, if appropriate.

Specific risks of interest will be defined by combinations of adverse event and/or other relevant safety data (e.g. lab data). The number (and proportion) of participants fulfilling such risk definitions will be summarized.

A participant with multiple adverse events within a primary system organ class will only be counted once towards the total of the primary system organ class.

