## 2.4 Treatments (study treatment, rescue medication, concomitant therapies, compliance)

### 2.4.1 Study treatment / compliance

The summary of exposure and time-at-risk will be based on the SAF.

**Duration of exposure to study drug** expressed in days is defined as the number of days spent on study treatment. Intermediate treatment interruptions will be subtracted from drug exposure, i.e. the duration of exposure to study treatment (in days) will be calculated as (last injection date – first injection date + 31 –  $\Sigma [(j+1)^{\text{th}} \text{ injection date} - j^{\text{th}} \text{ injection date} - 31]$ ), where j and j+1 refer to consecutive injections with injection dates more than 31 days apart.

Exposure to investigational study drug will be summarized with number and percentage of subjects by time category, and with summary statistics of the number of patient years of exposure.

Duration of exposure to study treatment will be summarized descriptively by duration category (i.e.  $\geq 1$  month,  $\geq 3$  months,  $\geq 6$  months,  $\geq 9$  months,  $\geq 12$  months). Descriptive statistics of duration in days will also be provided. The number of patient years is calculated as the sum of the duration of exposure for all subjects in the group.

**Time at risk** is the censoring time used for participants who did not experience the event of interest. For participants who have experienced the event of interest, the actual date of the SAE, or AE onset will be used.

- **Time at risk for AE** is defined as the number of days spent in the study, from first to last administration of study drug, plus the safety data cut-off of 100 days (or until EOS for participants continue with commercial ofatumumab immediately after EOS, or until last dose of study medication plus 100 days or one day before switching to another DMT, whichever comes earlier, for participants who have such switch in the PT FU). Time at risk for AE will be used for tables reporting AEs (including both SAE and non-SAE).
- **Time at risk for SAE** is defined as the number of days spent in the study from the day of first administration of study drug to the end of Post-treatment Follow-up period if the participant does not continue with commercial ofatumumab immediately after EOS. Time at risk for SAE will be used only for tables reporting SAEs.

Time at risk for AE and time at risk for SAE will be summarized in a similar way to duration of exposure to study drug.

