## **2.7      Safety analyses**

All safety analyses will be conducted using the SAF. The safety cutoff is defined as 100 days after the last dose administration of study drug (or EOS for participants continue with commercial ofatumumab immediately after EOS, or min(last dose of study medication + 100 days, date of switching to another DMT - 1) for participants who have such switch in the Post-treatment Follow-up period). Unless explicitly otherwise stated, only data up to and including the safety cut-off will be included in the analysis and data beyond this time point for a given subject will be excluded from the safety analysis.

The assessment of safety will be primarily based on the frequency of adverse events (including death and non-fatal serious adverse events). Additional safety assessments include laboratory tests and vital sign measures. Clinically significant findings in these additional safety assessments and other will be reported as adverse events and analyzed as such.

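### A switch to another DMT between the last dose and the EOS visit does not end the safety data as the same switch after EOS does; the effect is small and SAP wording can close it

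*SAP*

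**What the plan says.** **The cut-off.** SAP 2.1.1 (Table 2-1) starts from a default: "The safety cutoff is defined as 100 days after the last dose administration of study drug". It gives two exceptions. Participants who go straight on to commercial ofatumumab are cut at EOS. Participants who change to another DMT are cut at the earlier of last dose + 100 days and the "date of switching to another DMT - 1) for participants who have such switch in the Post-treatment Follow-up period". SAP 2.7 repeats this.

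**Time at risk.** SAP 2.4.1 uses the same condition for adverse events: "whichever comes earlier, for participants who have such switch in the PT FU".

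**Protocol.** Section 12.5.2 has the matching text, "date of switching to another DMT - 1) for participants who have such switch in the PT FU", and section 12.3 applies the same limit to time at risk.

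**When follow-up starts.** Protocol section 8 says that participants not continuing on commercial drug "will enter the 6-month Post-treatment Follow-up period after EOS as described in" Table 8-2, and the follow-up visits are set at EOS + 3 and EOS + 6 months.

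**When another DMT can start.** Protocol section 3 allows alternative MS therapy after study treatment is discontinued and does not require EOS to have taken place. Section 8 asks for EOS as soon as possible after an early stop, without a number of days. Footnote 11 of Table 8-1, the treatment-period schedule, provides for recording "any newly started MS treatment as applicable (for participants who have discontinued study medication".

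**The concern.** The cut-off depends on which study period the switch falls in, not on whether the participant is taking another drug. Two early discontinuers with the same last dose date and the same DMT start date are handled differently if one had the EOS visit just before the switch and the other just after it. For the second, events and measurements under the other drug are summarised as ofatumumab safety data.

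Safety is a secondary objective and the study has one arm, so no comparison group would show the admixture. The outputs at stake are the summaries of non-serious treatment-emergent adverse events, laboratory values and vital signs, and the summary of time at risk.

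**Working it through.** The plan gives no figure of its own for this point, so the check is a day count from its rule.

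**Inputs**
- Default cut-off: last dose + 100 days (SAP 2.1.1).
- Switch in follow-up: min(last dose + 100, switch date − 1) (SAP 2.1.1, 2.4.1, 2.7).
- Follow-up begins after EOS (protocol section 8).
- One month = 28 days (protocol sections 3 and 8). There is no dose at M12 (Table 8-1), so the last scheduled dose is at 11 × 28 = day 308.

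**Days on the other DMT that stay in.** Let the other DMT start d days after the last dose, with 1 ≤ d ≤ 100.
- Switch before EOS: the cut-off is last dose + 100, so the included days are 100 − d + 1 = 101 − d.
- Switch in follow-up: the cut-off is last dose + d − 1, so the included days are 0.

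| d | Before EOS | After EOS |
|---|---|---|
| 1 | 100 | 0 |
| 7 | 94 | 0 |
| 14 | 87 | 0 |
| 28 | 73 | 0 |
| 42 | 59 | 0 |

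**One hypothetical record.** Last dose day 140, other DMT from day 160 (d = 20), EOS day 168.
- As written, the cut-off is 140 + 100 = day 240, and days 160 to 240 are included: 101 − 20 = 81 days.
- With EOS on day 159 and all else equal, the cut-off is day 159 and no such days are included.
- Time at risk for this participant is 240 against 159 days: 240/159 − 1 = 51% longer.

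**Scheduled measurements.** Laboratory tests and vital signs are due at EOS (Table 8-1). If EOS falls after the switch and within the 100 days, those values are taken under the other drug and kept. The first follow-up visit, at EOS + 84 days, also falls inside the cut-off when EOS is no later than last dose + 16 (16 + 84 = 100).

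**Study level.** The documents do not say how many participants switch before EOS, so 1 to 5 of 100 is an assumption. As an approximate denominator, take 100 participants at 308 + 100 + 1 = 409 days each, or 40,900 person-days.
- 1 participant at 81 days: 81/40,900 = 0.2%.
- 5 participants at 81 days: 405/40,900 = 1.0%.
- 5 participants at the 100-day maximum: 500/40,900 = 1.2%.
- Outer bound, with all 15 participants in the 15% dropout allowance at 100 days: 1,500/40,900 = 3.7%.

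Participants who continue on commercial drug are cut at EOS, so the true denominator is smaller. At 336 days each it is 33,600, and the first two lines become 0.2% and 1.2%.

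**The case against.** **Follow-up might begin earlier.** Protocol section 3 and SAP 1.1 describe follow-up as lasting six months after the last dose. SAP Table 2-1 takes the end of the treatment period from the disposition page, not from the EOS visit. If follow-up began at the last dose, every later switch would already be cut. This stands as an ambiguity. It does not settle the matter, because protocol section 8 puts follow-up after EOS and both follow-up visits are timed from EOS.

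**The limit might be deliberate.** Ofatumumab's effects outlast dosing, so keeping the full 100 days can be defended. But neither document gives a reason for cutting at a switch after EOS and not at one before it, and the pharmacology is the same on both sides of that visit.

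**Few people, short windows.** This stands. EOS is mandatory and should follow discontinuation promptly.

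**Stronger readings that the documents do not support.**
- A reader might infer that serious outcomes are affected. SAP 2.1 and 2.7.1 include serious treatment-emergent events and deaths whatever the cut-off.
- A reader might infer that event rates are biased through an inflated denominator. SAP Amendment 1 removed exposure-adjusted rates, and SAP 2.7.1 reports numbers and percentages. Protocol 12.5.2 still describes such rates, so the point would return only if they were produced.
- A reader might take the 51% in the single record as a study-level effect. It describes one hypothetical participant.
- A reader might infer that data should end at any DMT start after the first dose. Where another DMT overlaps with dosing (Table 6-2 foresees this), such a cut would either drop data collected while ofatumumab was still being given or, if floored at the last dose, discard all later non-serious follow-up and still keep the overlap.

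**Conclusion.** The gap is real on the text of both documents. A switch after the last dose but before EOS leaves 101 − d days on another DMT in the ofatumumab safety data; the same switch after EOS leaves none. This rests on follow-up starting after EOS, which is the better-supported reading but not the only one.

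The effect is small: about 0.2–1% of total adverse-event time at risk if 1 to 5 of 100 participants are affected, a number that is assumed because the documents give none. It reaches non-serious events, laboratory and vital-sign summaries and the time-at-risk summary. It does not reach the primary endpoint or, under the SAP, whether serious events and deaths are included. It is worth correcting because the correction is cheap and removes a dependence on visit order, not because the safety conclusions are in doubt.

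**What to change.** In SAP 2.1.1 and 2.7, replace "for participants who have such switch in the Post-treatment Follow-up period" with: *for participants who start another DMT after the last dose of study drug, whether before or after the EOS visit*. Make the same change to the follow-up condition in SAP 2.4.1. The cut-off is then min(last dose + 100 days, DMT start − 1), and the days on the other DMT are 0 for every d ≥ 1.

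If another DMT starts on or before the last dose date, keep last dose + 100 days and list these participants with the overlap flagged.

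Record the change in SAP section 4, which now reads as not applicable. No protocol amendment is needed.

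**Cost.** Three wording changes, one note and one listing; newly started MS treatment is already collected. A few early discontinuers lose some non-serious safety follow-up from the summaries. Their later treatment-emergent events would still appear, because SAP 2.7.5 lists events beyond the cut-off for participants who stop treatment early.
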